8.1 Definition of Protocol Deviations and Analysis Sets

Important protocol deviations (IPDs) are protocol deviations that might significantly affect the completeness, accuracy, and/or reliability of the study data or that might significantly affect a subject's rights, safety, or well-being.

IPDs include:

- Subjects that are dosed on the study despite not satisfying the inclusion criteria;
- Subjects that develop withdrawal criteria whilst on the study but are not withdrawn;
- Subjects that receive the wrong treatment or a significantly incorrect dose;
- Subjects that receive an excluded concomitant medication;
- Deviation from Good Clinical Practice (GCP).

The following deviations will be identified and confirmed prior to or at the Data Review Meeting at the latest.

- IPDs as defined above
- Deviations from the inclusion and exclusion criteria
- Deviations post inclusion

All IPDs will be documented in the study data tabulation model (SDTM) datasets whether identified through site monitoring, medical review or programming.

8.2 Definition of Analysis Sets and Subgroups

Screening Analysis Set (SCR)

The screening analysis set includes all subjects who signed the informed consent.

Full Analysis Set (FAS)

The full analysis set (FAS) will include all enrolled subjects who receive any dose of avelumab.

Safety Analysis Set (SAF)

The safety analysis set (SAF) will include all enrolled subjects who were administered any dose of avelumab. Analyses performed on the safety set will consider subjects as treated. In this non-randomized study, the FAS and the SAF will be identical.

Dose Limiting Toxicity (DLT) Analysis Set

The DLT analysis set includes all subjects who meet either of the following criteria:

- Have received 100% of all planned doses of treatment during the DLT evaluation period (first 2 cycles of treatment) and have been followed for at least 28 days
- Have stopped treatment because of a DLT in the DLT evaluation period

Pharmacokinetic (PK) Analysis Set

The PK Analysis Set will consist of all subjects who receive at least one dose of avelumab, have no important protocol deviations or important events affecting PK, and provide at least one measurable post-dose concentration. Subjects will be analyzed according to the actual treatment they received. All PK analyses will be based on this analysis set.

Immunogenicity Analysis Set

The immunogenicity analysis set will include all subjects who receive any dose of avelumab and who have at least one valid ADA result (including negative, positive-TNR).

Biomarker Analysis Set

Biomarker analysis set will include all subjects who receive any dose of avelumab and who have provided at least one blood, serum, plasma, or tumor sample for biomarker assessments.

Table 1 summarizes the use of the analysis sets in the different analyses.

Table 1 Statistical Analysis by Analysis Set

Analyses	Screening Analysis Set	Full Analysis Set	Safety Analysis Set	DLT Analysis Set	PK Analysis Set	Immunogenicity Analysis Set	Biomarker Analysis Set
Baseline Characteristics	✓	✓	✓				
Prior and Concomitant Therapies		✓	✓				
Compliance and Exposure			✓				
Primary Endpoint			✓	✓			
Secondary Endpoint		✓			✓	✓	✓
CCI							
Safety			✓				

9 General Specifications for Data Analyses

[figure not shown]
Throughout this document “start date” is the date of first dose of study treatment.

Data handling after cut-off date:

Data after the cut-off may not undergo the cleaning process and will not be displayed in any listings or used for summary statistics, statistical analyses or imputations.

Pooling of centers:

Because of the high number of participating centers and the anticipated small number of subjects treated in each center data will be pooled across centers, and the factor center will not be considered in statistical models or for subgroup analyses.

Presentation of continuous and qualitative variables:

Continuous variables will be summarized using descriptive statistics, i.e.

- number of subjects (N), number of subjects with non-missing values, number of subjects with missing values,
- mean, standard deviation,
- median, 25th Percentile, 75th Percentile (Q1, Q3),
- minimum, and maximum.

Qualitative variables will be summarized by counts and percentages.

Unless otherwise stated the calculation of proportions will be based on the number of subjects of the analysis set of interest. Therefore counts of missing observations will be included in the denominator and presented as a separate category.

In case the analysis refers only to certain visits, percentages will be based on the number of subjects still present in the study at that visit, unless otherwise specified.

Definition of baseline:

The last available assessment prior to the start of study treatment is defined as “baseline” value or “baseline” assessment for safety and efficacy analyses. If an assessment is planned to be performed prior to the first dose of study treatment in the protocol and the assessment is performed on the same day as the first dose of study treatment, it will be assumed that it was performed prior to study treatment administration, if assessment time point is not collected or is missing. If assessment time points are collected, the observed time point will be used to determine pre-dose on study day 1 for baseline calculation. Unscheduled assessments will be used in the determination of baseline. However, if time is missing, an unscheduled assessment on study day 1 will be considered to have been obtained after study treatment administration.

If both central and local labs are collected in the study, the baseline will be derived based only on the central lab collected data.

Subjects who start treatment and discontinue from the study on the same day may have two different sets of data collected on study day 1 (one during study and one in the End of Treatment (EOT) visit). Data reported at the EOT visit are not eligible for baseline selection.

If a scheduled pre-dose measurement actually occurred post-dose, then the corresponding measurement will be treated and analyzed similar to an unscheduled post-dose measurement.

Baseline for HR and QT/QTc assessments will be derived from the visit where both HR and QT are not missing. QTcF will be derived based on HR and QT.

Definition of study day:

Study day is defined relative to the date of start of treatment. Study day 1 defines the day of first administration with avelumab, the day before is defined as study day -1 (no study day 0 is defined).

Definition of on-treatment period:

The on-treatment period is defined as the time from the first dose of study treatment through minimum (30 days + last dose of study treatment, start day of new anti-cancer drug therapy - 1 day).

The date of new anti-cancer drug therapy after start date is derived as outlined in Section 12.1.

Definition of duration:

Duration will be calculated by the difference of start and stop date + 1 (e.g. survival time (days) = date of death - date of first dose of study drug + 1).

The time since an event (e.g. time since first diagnosis) will be calculated as reference date minus date of event.

Standard derivations and reporting conventions:

The following conversion factors will be used to convert days into months or years:

1 week = 7 days, 1 month = 30.4375 days, 1 year = 365.25 days.

Demographic and physical measurements:

- Age [years]:
 - (date of given informed consent - date of birth + 1) / 365.25
 - In case only year and month of birth are given: Age [years]: (year/month of given informed consent - year/month of birth) / 12
 - In case only year of birth is given: Age [years]: (year of given informed consent - year of birth)

The integer part of the calculated age will be used for reporting purposes.

- BMI (kg/m^2) = weight (kg)/[height (m)]².
- BSA (m^2) = ([height (cm) × weight (kg)] / 3600)^{0.5} (1)

For reporting conventions, mean and median should generally be displayed one more decimal place than the raw data and standard deviation should be displayed to two more decimal places than the raw data. Percentages will be reported to one decimal place. The rounding will be performed to closest integer / first decimal using the common mid-point between the two

consecutive values. E.g. 6.1 to 6.4 will be rounded to an integer of 6, and 6.5 to 6.9 will be rounded to an integer of 7.

Unscheduled visits:

Generally, data collected at unscheduled visits will be included and analyzed for both safety and efficacy analyses in the same fashion as the data collected at scheduled visits except where otherwise noted in the sections that follow. Descriptive statistics (mean, SD, median, minimum, maximum, quartiles) by nominal visit or time point for safety endpoints such as laboratory measurements, ECGs and vital signs will include only data from scheduled visits.

Handling of missing data and imputation rules:

Unless otherwise specified, all data will be evaluated as observed, and no imputation method for missing values will be used.

In all subject data listings imputed values will be presented. In all listings imputed information will be flagged.

Missing statistics, e.g. when they cannot be calculated, should be presented as 'ND' or 'NA'. For example, if N=1, the measure of variability (SD) cannot be computed and should be presented as 'ND'.

Disease history:

Incomplete dates for disease history (e.g. initial diagnosis date, date of documented, metastatic disease diagnosis, date of response or progression in prior treatment) will be imputed as follows:

- If the day is missing, it will be imputed to the 15th day of the month.
- If both day and month are missing and the year is prior to the year of the first study treatment, the month and day will be imputed as July 1st.
- If both day and month are missing and the year is same as the year of the first study treatment, the month and day will be imputed as January 1st.
- If the date is completely missing, no imputation will be performed.
- For all imputed disease history dates, the imputed date will be set equal to the maximum of the imputed date as specified above and the subject's date of birth.

Adverse events:

Incomplete AE-related dates will be imputed as follows:

- If the AE onset date is missing completely, then the onset date will be replaced by the start of study treatment.
- If only the day part of the AE onset date is missing, but the month and year are equal to the start of study treatment, then the AE onset date will be replaced by the start of study

treatment. For example, if the AE onset date is --/JAN/2015, and study treatment start date is 15/JAN/2015, then the imputed AE onset date will be 15/JAN/2015.

- If both the day and month of the AE onset date are missing but the onset year is equal to the start of study treatment, then the onset date will be replaced by the start of study treatment. For example, if AE onset date is --/--/2014, and study treatment start date is 19/NOV/2014, then the imputed AE onset date will be 19/NOV/2014.
- In all other cases the missing onset day or missing onset month will be replaced by 1.
- For all imputed AE start dates, the imputed date will be set equal to the maximum of the imputed date as specified above and the subject's date of birth.
- Incomplete stop date will be replaced by the last day of the month (if day is missing only), if not resulting in a date later than the date of subject's death. In the latter case the date of death will be used to impute the incomplete stop date.
- In all other cases the incomplete stop date will not be imputed. If stop date of AE is after date of cut-off outcome of AE is ongoing at cut-off.

Prior and concomitant medications:

Incomplete prior/concomitant medication start dates will be imputed as follows:

- If the medication start date is missing completely, then the medication start date will be replaced by the start of study treatment.
- If the day of medication date is missing, but the month and year are equal to the start of study treatment, then the medication start date will be replaced by the start of study treatment. For example, if the medication start date is --/JAN/2015, and study treatment start date is 15/JAN/2015, then the imputed medication start date will be 15/JAN/2015.
- If both the day and month of medication start date are missing but the start year is equal to the start of study treatment, then the medication start date will be replaced by the start of study treatment. For example, if the medication start date is --/--/2014, and study treatment start date is 19/NOV/2014, then the imputed medication start date will be 19/NOV/2014.
- In all other cases the missing medication day or missing medication month will be replaced by 1.
- For all imputed prior/concomitant start dates, the imputed date will be set equal to the maximum of the imputed date as specified above and the subject's date of birth.
- Incomplete stop date will be replaced by the last day of the month (if day is missing only), if not resulting in a date later than the date of subject's death. In the latter case the date of death will be used to impute the incomplete stop date.
- In all other cases the incomplete medication stop date will not be imputed.

In case an imputed medication start date is later than the medication stop date, it will be replaced by the medication stop date.

Subsequent anti-cancer therapy

Incomplete subsequent anti-cancer therapy start dates will be imputed as follows:

- If only day is missing, it will be imputed as the last day of the month unless the end date of subsequent anti-cancer therapy is before that date. In that case, the incomplete anti-cancer therapy start date will be imputed as the end date of the anti-cancer therapy.
- If both day and month are missing, no imputation will be performed.

Exposure:

- In case the study drug start date is missing, no imputation will be performed.
- In case the last date of study drug is incomplete the date of last administration of study drug will be taken from the treatment termination eCRF pages.

Date of last contact:

The date of last contact will be derived for subjects not known to have died at the analysis cut-off using the latest complete date among the following:

- All subject assessment dates (blood draws (laboratory, PK), vital signs, performance status, ECG, tumor assessments)
- Start and end dates of anti-cancer therapies administered after study treatment discontinuation.
- AE start and end dates
- Date last known to be alive collected on the eCRF form "Subject Status / Survival Follow-up" Study drug start and end dates
- Date of discontinuation on disposition eCRF pages (do not use if reason for discontinuation is lost to follow-up).

Only dates associated with actual examinations of the subject will be used in the derivation. Dates associated with a technical operation unrelated to subject status such as the date a blood sample was processed will not be used. Assessment dates after the cut-off date will not be applied to derive the last contact date.

Death Date:

Missing or partial death dates will be imputed based on the last contact date:

- If the date is missing it will be imputed as day after date of last contact
- If the day or both day and month is missing, death will be imputed to the maximum of the full (non-imputed) day after the date of last contact and the following:
 - Missing day: 1st day of the month and year of death
 - Missing day and month: January 1st of the year of death

If the day is missing from the date of last contact it will be imputed to 1st day of the month and year of last contact only if derived from the survival page.

Tumor Assessments:

All investigation dates (e.g. X-ray, computed tomography (CT) scan) must be completed with day, month and year.

If there are multiple scan dates associated with an evaluation, i.e., radiological assessments occur over a series of days rather than the same day, the choice of date of assessment could impact the date of progression and/or date of response. If there are multiple scan dates associated with an evaluation, the earliest of the scan dates associated with the evaluation will be used as the date of assessment.

If one or more investigation dates for an evaluation are incomplete but other investigation dates are available, the incomplete date(s) are not considered for calculation of the assessment date and assessment date is calculated as the earliest of all investigation dates (e.g. X-ray, CT-scan).

If all measurement dates for an evaluation have no day recorded, the 1st of the month is used.

If the month is not completed, for any of the investigations for an evaluation, the respective assessment will be considered to be at the date which is exactly between the previous and the following assessment. If both a previous and following assessments are not available, this assessment will not be used for any calculations.

All statistical analyses will be performed using SAS® Version 9.2 or higher.

10 Study Subjects

The subsections in this section include specifications for reporting subject disposition and treatment/study discontinuations. Additionally procedures for reporting protocol deviations are provided.

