Treatment can continue past the initial determination of confirmed disease progression (see Section 6.2).

Subjects who have experienced a complete response (CR) should be treated for a minimum of 12 months based on clinical judgment of benefit and/or until confirmed progression per irRECIST (Bohnsack 2014), unacceptable toxicity, or any criterion for withdrawal occurs, after confirmation of response as specified in this protocol. In case a subject with a confirmed CR relapses after stopping treatment, during long-term follow-up but prior to the End of Trial, 1 re-initiation of treatment will be allowed at the discretion of the Investigator and agreement of the Medical Monitor. In order to be eligible for retreatment, the subject must not have experienced any toxicity that led to treatment discontinuation of the initial avelumab therapy. Prior to re-initiation of the study treatment, malignant disease will be radiologically re-staged to assess all known sites of the disease and to establish a new baseline for subsequent tumor measurements. Relevant safety laboratory results must be available and verified prior to re-initiating treatment. Subjects who re-initiate treatment will stay on study and will be treated and monitored according to the protocol and the Schedule of Assessments (Table 1).

The primary Phase I endpoints are:

- Occurrence and severity of treatment-emergent adverse events (TEAEs)  $\geq$  Grade 3 according to NCI-CTCAE v4.03
- DLTs to determine the RP2D

Safety endpoints include incidence of AEs and laboratory abnormalities assessed throughout the trial and evaluated using the National Cancer Institute Common Terminology Criteria for Adverse Events (NCI-CTCAE) v4.03, and vital signs.

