10.1 Disposition of Subjects and Discontinuations

The following will be summarized overall and by dose level.

The percentages below will be calculated based on the number of subjects in the FAS.

- Total number of subjects screened
- Number of subjects who screen failed prior to enrollment overall and by reason for screen failure
- Number and percentage of treated subjects in the following populations:
 - FAS
 - Safety analysis set

- DLT analysis set
- Immunogenicity analysis set
- PK analysis set
- Biomarker analysis set
- Number of treated subjects
- Number of subjects that received no treatment
- Number and percentage of subjects still on treatment
- Number and percentage of subjects who discontinued treatment overall and per reason of treatment discontinuation
- Number and percentage of subjects who discontinued the treatment but are still in follow-up
- Number and percentage of subjects who re-initiated avelumab treatment and discontinued treatment after re-initiation
- Number and percentage of subjects who discontinued the trial overall and by the main reason for discontinuation

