13.1 Exposure to Study Drug

The dose level for avelumab is calculated as actual dose administered/weight (mg/kg). The last available weight of the subject on or prior to the day of dosing will be used.

The duration of avelumab treatment (in weeks) during the study for a subject is defined as:

$$\text{Treatment duration (weeks)} = (\text{last dose date} - \text{first dose date} + 14) / 7$$

The cumulative dose (mg/kg) of avelumab per subject in a time period is the sum of the actual dose levels that the subject received within that period (i.e., total dose administered (mg) / weight (kg)).

Each cycle for avelumab is defined by a 2-week period. The dose intensity (DI) and the relative dose intensity (RDI) will be calculated for each subject across all cycles. The dose intensity per cycle (mg/kg/cycle) is defined as

$$\text{DI (mg/kg/cycle)} = \text{Cumulative dose (mg/kg)} / [\text{duration of therapy (in weeks)} / 2]$$

The relative dose intensity (RDI) is defined as the actual dose intensity divided by the planned dose as specified in the protocol per cycle, denoted in the formula below as “xx”, and expressed in %. The dose level will be determined via the escalation process.

$$\text{RDI (\%)} = 100 \times [\text{DI (mg/kg/cycle)} / \text{xx (mg/kg)}]$$

The summary of treatment exposure and compliance for avelumab will include the following information:

- Treatment duration (weeks)
- Total number of infusions received
- Cumulative dose (mg/kg)
- Dose intensity (mg/kg/cycle)
- Relative dose intensity (%)

A listing of study treatment administration will be provided and will include subject identifier, age, study day, start date and time of the infusion as well as the kit number.

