15.4 Clinical Laboratory Evaluation

15.4.1 Hematology and Chemistry Parameters

Treatment emergent laboratory assessments are any sample collected after the first dose of study treatment administration and within 30 days from the last study treatment administration.

Laboratory results will be classified according to the NCI-CTCAE criteria version 4.03. Non-numerical qualifiers (with the exception of fasting flags) will not be taken into consideration in the derivation of CTCAE criteria (e.g., hypokalemia Grade 1 and Grade 2 are only distinguished by a non-numerical qualifier and therefore Grade 2 will not be derived). Additional laboratory results that are not part of NCI-CTCAE will be presented according to the categories: below normal limit, within normal limits and above normal limit (according to the laboratory normal ranges).

The worst on-treatment grade (i.e. on or after first study treatment administration and within 30 days after last study treatment administration) will be summarized considering only subjects with post baseline laboratory samples: Laboratory tests by NCI-CTCAE grade (0, 1, 2, 3, 4, any).

Abnormalities classified according to NCI-CTCAE toxicity grading version 4.03 are a secondary endpoint for this study and will be described by dose level using the worst grade. For those parameters which are graded with two toxicities such as potassium (hypokalemia/hyperkalemia), the toxicities will be summarized separately. Low direction toxicity (e.g., hypokalemia) grades at baseline and post baseline will be set to 0 when the variables are derived for summarizing high direction toxicity (e.g., hyperkalemia), and vice versa.

For **WBC differential counts** (total neutrophil [including bands], lymphocyte, monocyte, eosinophil, and basophil counts), the absolute value will be used when reported. When only percentages are available (this is mainly important for neutrophils and lymphocytes, because the CTCAE grading is based on the absolute counts), the absolute value is derived as follows:

$$\text{Derived differential absolute count} = (\text{WBC count}) * (\text{Differential \%value} / 100)$$

If the range for the differential absolute count is not available (only range for value in % is available) then Grade 1 will be attributed to as follows:

- Lymphocyte count decreased:
 - derived absolute count does not meet Grade 2-4 criteria, and
 - % value < % LLN value, and
 - derived absolute count $\geq 800/\text{mm}^3$

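### SAP 13.1 counts the off-drug interval before a permitted re-initiation as treatment, overstating duration and understating DI and RDI; the single on-treatment window mishandles the same interval

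*SAP*

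**What the plan says.** **Restart.** Protocol 5.1.1.1 says that children with a CR "should be treated for a minimum of 12 months based on clinical judgment of benefit". If a confirmed CR relapses after treatment has stopped, "1 re-initiation of treatment will be allowed at the discretion of the Investigator and agreement of the Medical Monitor". It adds: "Subjects who re-initiate treatment will stay on study and will be treated and monitored according to the protocol". Sections 5.1.1.2, 6.2.1 and 7.1.2 repeat the permission. Safety laboratory results must be checked before dosing resumes.

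**Where the SAP recognises it.** Section 10.1 tabulates "Number and percentage of subjects who re-initiated avelumab treatment and discontinued treatment after re-initiation". I found no other mention of re-initiation in the SAP.

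**Exposure (SAP 13.1).** "The duration of avelumab treatment (in weeks) during the study for a subject is defined as" (last dose date − first dose date + 14)/7. DI is cumulative dose divided by half that duration, and RDI is DI as a percentage of the planned dose per cycle. Section 13.3 shows intervals longer than 14 days in a listing only.

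**On-treatment period (SAP 9).** There is one period per subject: "The on-treatment period is defined as the time from the first dose of study treatment through minimum (30 days + last dose of study treatment", or the day before new anti-cancer drug therapy if that is earlier. Section 12.1 takes the earliest such date. Protocol 8.5.1 and 8.5.2.1 define a single window of the same kind, each allowing for exceptions stated elsewhere.

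**Laboratory window (SAP 15.4.1).** "Treatment emergent laboratory assessments are any sample collected after the first dose of study treatment administration and within 30 days from the last" administration. It has no cut-off for new therapy.

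None of these definitions identifies first and last dose by course or removes the off-drug interval.

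**The concern.** For a child who restarts, the last dose is the last dose of the second course. Three consequences follow.

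1. *Exposure.* The whole gap enters duration and the denominators of DI and RDI. A child who missed no planned dose in either course appears to have been poorly dosed.
2. *Classification by a later decision.* An adverse event or laboratory sample more than 30 days after course 1 is off-treatment if the child never restarts, and treatment-emergent if the child does. The event and its timing relative to dosing are identical. Such data can exist: SAEs are collected to the 90-day call, related SAEs at any time (Protocol 7.4.1.3), and laboratory results are needed before the restart.
3. *The opposite error.* If a new anti-cancer drug starts during the gap, the section 9 window closes before the restart, and adverse events under renewed avelumab are not treatment-emergent.

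At stake are the exposure table and, for such a child, the classification of events that feed the TEAE and worst-laboratory-grade summaries.

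**Working it through.** The plan states no figure to reproduce, so the SAP formulas are applied to an illustrative subject.

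**Inputs**
- Dose 10 mg/kg every 2 weeks (Protocol 5.1.1.1, starting dose).
- Course 1 of 26 doses, reflecting the 12-month minimum in Protocol 5.1.1.1.
- Course 2 of 6 or 13 doses, and a gap of g weeks after the last 14-day interval of course 1. **These are assumptions**; the documents give neither. All doses are full and on schedule.

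**Check on one uninterrupted course.** 26 doses: (25 × 14 + 14)/7 = 52 weeks. Cumulative dose is 260 mg/kg, DI = 260/26 = 10 mg/kg/cycle and RDI = 100%, as it should be.

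**Two courses, 26 + 6 doses**
- First to last dose = 25 × 14 + (14 + 7g) + 5 × 14 = 434 + 7g days.
- Duration under SAP 13.1 = (434 + 7g + 14)/7 = 64 + g weeks.
- Cumulative dose = 320 mg/kg, so DI = 320/[(64 + g)/2] and RDI = 100 × 64/(64 + g).
- By course: 52 + 12 = 64 weeks and RDI 100%, whatever the gap.

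Days that lie after last course-1 dose + 30 and before the restart number (14 + 7g) − 30 − 1 = 7g − 17. The single window adds these to the on-treatment period if no new drug intervenes.

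| Gap (weeks) | Duration, SAP 13.1 (weeks) | DI (mg/kg/cycle) | RDI | Off-drug days added to the on-treatment period |
|---|---|---|---|---|
| 8 | 72 | 8.89 | 88.9% | 39 |
| 12 | 76 | 8.42 | 84.2% | 67 |
| 26 | 90 | 7.11 | 71.1% | 165 |
| 52 | 116 | 5.52 | 55.2% | 347 |

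**Longer second course, 26 + 13 doses.** By course this is 78 weeks and RDI 100%. SAP 13.1 gives 86 weeks and 90.7% (8-week gap), 104 weeks and 75.0% (26 weeks), and 130 weeks and 60.0% (52 weeks).

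**Event classification.** Take an SAE on Day 60 after the last course-1 dose. Without a restart it is outside the window, since 60 > 30. With a 12-week gap the restart falls on Day 14 + 84 = 98, the single window spans Day 60, and the SAE is treatment-emergent.

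**New drug in the gap.** If a new anti-cancer drug starts on Day 60 instead, the window ends on Day 59, and every course-2 event from Day 98 on falls outside it. The re-initiation text neither requires nor excludes an intervening drug.

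**The case against.** The strongest reply is that this path is narrow. It needs a confirmed CR, a first course meant to last at least 12 months, a stop, relapse before the end of the trial, no toxicity that ended the first course, and agreement to restart. SAP version 2.0 covers Phase I only, and section 14.2 provides for there being no responders at all. Nothing in the documents shows that any child restarted. This stands and limits the size of the point.

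Also fair:
- *The SAP follows the protocol's window.* True of the on-treatment period. But protocol 8.5.1 and 8.5.2.1 leave room for exceptions, so the SAP can refine it.
- *RDI is not an endpoint.* True. Number of infusions and cumulative dose are correct as defined, and the long interval appears in a listing. The tabulated duration, DI and RDI would still be wrong.
- *The rule errs on the inclusive side for safety.* Partly true, and the irAE case definition in SAP Appendix I itself accepts onset up to 90 days after the last dose. It fails when a new drug starts in the gap, because course-2 events are then left out.

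A reader might infer that the primary Grade ≥ 3 TEAE endpoint is seriously distorted. The documents do not support that. SAP 15.2 counts subjects, so a gap event changes the overall count only if the child had no other Grade ≥ 3 TEAE. Routine collection ends at the 90-day call, so a long gap yields few recorded events. A reader might also infer that one such child must set the maximum duration and minimum RDI. That does not follow: 64 dosed weeks may already be the maximum, another child may have a lower RDI, and medians and quartiles would barely move.

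**Conclusion.** The point holds as a minor derivation error. The protocol permits a restart and the SAP counts those who restart, yet the SAP's exposure formulas give a wrong answer for them. RDI becomes 64/(64 + g) in the 26 + 6 illustration, about 55% to 89% for gaps of 52 down to 8 weeks, when no planned dose was missed. These figures rest on assumed course and gap lengths; the direction does not.

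The window problem is separate. Section 13.1 does not use the 30-day on-treatment period, so correcting one definition leaves the other as it is. The window also does not always absorb the whole gap: a new anti-cancer drug closes it early, which reverses the error.

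Only re-treated subjects are affected, few and possibly none. If nobody restarted, no reported number changes. DLT evaluation uses the first 28 days, so it and the RP2D are unaffected, and any change to the Grade ≥ 3 TEAE count is small.

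**What to change.** 1. **SAP 13.1.** Compute duration as the sum over courses of (last dose − first dose + 14)/7, and base DI and RDI on that sum. Delays within a course stay in the duration.
2. **SAP 9 and 15.4.1.** Define the on-treatment period as the union of courses, each from its first dose to its last dose + 30 days. For section 9, end a course's period earlier, on the day before the first new anti-cancer drug therapy that starts after that course's first dose (and, for course 1, before re-initiation). Tying the cut-off to each course stops a drug given in the gap from giving course 2 an end date before its start.
3. **SAP 7.** Record this as a refinement of protocol 8.5.1 and 8.5.2.1.

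The cost is a few lines of text and a course flag in the exposure dataset. The downside is that adverse events between courses, beyond the 30-day tail, move from the tables to the listings, where SAP 15.2 already flags off-treatment events. The tabulated safety counts become slightly less inclusive.
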